Subjects that are diagnosed with a UTI while on study treatment and prior to the TOC Visit (between Day 6 and Day 11-14 TOC Visit) will be considered treatment failures and do not have to return for the TOC Visit but they will be asked to return for the Day 24-30 Outcome Assessment Visit and receive the Day 38-44 phone call. Similarly, subjects that are diagnosed with a UTI at any time after the TOC Visit through the Day 38-44 call will continue to return for the Outcome Assessment Visit and receive the Day 38-44 follow-up phone call. A stool specimen will still be collected at the Outcome Assessment Visit for these subjects diagnosed with UTIs (either before or after TOC).

Sub-studies

Seattle Children’s Hospital R21

An R21-funded sub-study titled, “Differences in infecting and colonizing Enterobacteriaceae from short-course vs. standard therapy of pediatric UTI” is being performed with collaborators at Seattle Children’s Hospital. This sub-study hypothesizes that both the antibiotic agent and the length of therapy will affect the patients’ indigenous flora and thus affect both the likelihood of recovering *E. coli* and/or *K.*

pneumoniae from stool and the resistance phenotypes of the recovered isolates. The sub-study will utilize PCR- and sequence-based methods to characterize phylogenetic and resistance properties of the recovered isolates.

Carbapenem resistant enterobacteriaceae

For each enrolled research subject, the stool or perirectal swab collected at the Test of Cure visit will also be utilized to perform additional screening for the presence of carbapenem resistant enterobacteriaceae. The results of this additional screening will be used to determine the prevalence of colonization with carbapenem-resistant Enterobacteriaceae (overall and for specific pathogens) in ambulatory children after completion of treatment for UTI.

Microbiome pilot study

For each subject at CHOP who agrees to participate in the Microbiome pilot study, an additional perirectal swab and anal swab will be collected. The additional swabs will be collected at each visit and will be used to determine the composition of the subjects' microbiome. For subjects in diapers, an additional stool swab will also be collected. The accuracy of microbiome analysis resulting from perirectal swabs will be tested via comparison with analysis performed on stool specimens. The anal swab will be used to assess the presence of skin flora contamination in the peri-rectal swabs.

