4.2.1 Primary and Secondary Outcome Measures

The primary outcome measure is:

- Comparison of efficacy based on symptomatic UTI as assessed at the TOC visit (Day 11-14), between short-course and standard-course of antibiotics.

Since the primary objective of the study is to establish that short-course therapy is as effective as the standard therapy, the analysis of the primary endpoint will be based on a non-inferiority test. The primary analysis will be done on the intent to treat (ITT) population.

The secondary outcome measures are:

- Comparison of the number of subjects that have a recurrent infection (includes a relapse UTI or a reinfection) at any time after the TOC visit (Day 11-14), following short-course versus standard-course of antibiotics.
- Comparison of the number of subjects that become colonized with antimicrobial resistant *Escherichia coli* (*E. coli*) and *Klebsiella pneumoniae* (*K. pneumoniae*) in the gastrointestinal tract as assessed through Day 24-30, following short-course versus standard course of antibiotics.
- Comparison of the number of subjects with asymptomatic bacteriuria at the TOC visit, following short-course versus standard-course of antibiotics.

-
- Comparison of the number of subjects with clinical symptoms that may be related to a UTI prior to or at the TOC visit, following short-course versus standard-course of antibiotics.
 - Comparison of the number of subjects with positive urine cultures prior to or at the TOC visit, following short-course versus standard-course of antibiotics.

For a summary of individual subject study outcomes against the primary outcome measure see Table 2.

Sub-study Outcome Measures:

Seattle Children’s Hospital R21

- Presence of *E. coli*, presence of *K. pneumoniae*
- Sub-types of *E. coli* (0=phylogroups A or B1, 1=phylogroups B2 or D), sub-types of *K. pneumoniae*
- Presence of treatment-susceptible *E. coli*, presence of treatment-susceptible *K. pneumoniae*
- Presence of treatment-resistant *E. coli*, presence of treatment-resistant *K. pneumoniae*

Carbapenem resistant Enterobacteriaceae study

- Prevalence of colonization with carbapenem resistant *Enterobacteriaceae* in children after completion of the course of antibiotic therapy for UTI

Microbiome pilot study

- Comparison of the overall biodiversity of the gut microbial community, as measured by culture-independent marker gene sequencing at each follow-up visit following short-course and standard-course antibiotic exposure.

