For each subject at CHOP who agrees to participate in the Microbiome pilot study, an additional perirectal swab and an anal swab will be collected. Subjects in diapers will also have a third additional stool swab collected if a soiled diaper can be obtained. The additional swabs will be collected at each visit and will be used to determine the composition of the subjects’ microbiome. Microbiome composition will be quantified using high-throughput DNA amplicon sequencing of 16S ribosomal RNA genes. The accuracy of microbiome analysis resulting from perirectal swabs will be tested via comparison with analysis performed on stool specimens. All samples will be shipped immediately or frozen overnight prior to shipment to collaborators at the University of Minnesota. Additionally, subjects agreeing to participate will be asked to complete a questionnaire providing data about feeding (breast milk, formula, timing of introduction of solid foods); most recent antibiotic prescriptions (name, dose, and duration); and number of antibiotic courses in life.

Spectrum of Stool Bacteria

For each enrolled research subject, the stool or perirectal swab collected at each visit will be used to identify any organisms present in the stool in addition to the organisms of interest for the SCOUT study, *E. coli* and *K. pneumoniae*. These organisms that grow from SCOUT stool cultures are already identified as a result of the processing taking place for the SCOUT study. In

this sub-study, the names of these other bacteria will be collected in a database to allow for a general description of the organisms that are present in children that are receiving antibiotic therapy for a urinary tract infection.

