8.2 Enrollment Visit (Day 2-6 from start of prescribed antibiotics)

Prior to taking the sixth day of prescribed treatment

The Study Nurse/Nurse Practitioner/Physician will discuss the SCOUT Study, the goal, the study procedures and risks with the parent(s)/legal guardian(s); answer any questions and address any concerns that they have; have the parent(s) or guardian(s) sign the informed consent form and the child sign the assent form (if \geq seven years of age and enrolled at CHOP) if applicable prior to any study procedures being performed. Study Nurses/Nurse Practitioners/Physicians will also administer the eligibility questionnaire; administer a symptom questionnaire to confirm by history clinical

improvement (afebrile within 24 hours and asymptomatic [absence of dysuria in all children; absence of suprapubic, abdominal or flank pain, urinary urgency, frequency, hesitancy, dysuria in children >2 years and absence of poor feeding or vomiting in children >2 months to 2 years]); take the child’s temperature; and perform a targeted pain assessment for any suprapubic, abdominal, or flank pain/tenderness. In addition, a baseline stool sample will be collected and concomitant medications will be reviewed.

The written consent and assent documents, acquired from subject’s parent(s) or legal guardian(s) and subject (if age seven or older and enrolled at CHOP) before any study procedures are performed and the child is enrolled in the study, will describe potential risks and benefits of study participation as well as the responsibilities of the study participants, parent(s) or legal guardian(s), and study investigators. This assent document will be written in language understandable to the child (age seven or older).

At the Enrollment Visit, after a potential subject has met the study eligibility criteria, including exhibiting clinical improvement (afebrile and asymptomatic), the child will be given a random treatment assignment to either short-course or standard-of-care therapy. Subjects will be randomized based on the responses of the Study Nurse/Nurse Practitioner or Physician to the WesTrax™ interactive voice response (IVR) system. The system will stratify randomization based on whether:

- (1) The UTI was originally associated with fever and
- (2) The antibiotic prescribed at initiation of therapy.

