If the Enrollment Visit occurs at any time prior to completion of the day 5 dosing of prescribed antibiotic treatment, the child’s parent(s)/legal guardian(s) will be advised to complete their originally prescribed medication through day five. The subject would start study product on Day 6 and continue through Day 10. For these subjects enrolled prior to Day 5, confirmation from the parents will be obtained on Day 5 or Day 6 (prior to taking the first dose of SCOUT therapy on Day 6) that the subjects remain afebrile and have not had worsening of symptoms. Any volunteer that develops a fever or worsening symptoms prior to initiating study treatment will be considered an entry failure. If the Enrollment Visit occurs on Day 6, the Study Coordinator will clearly explain that the Enrollment Visit can only occur on Day 6 of antibiotic treatment if the child has not yet started the Day 6 dose of the initially prescribed antibiotics. The Study Nurse/Nurse Practitioner/Physician will confirm (at the Enrollment Visit) that the child has not yet started their Day 6 dose of prescribed antibiotics prior to enrolling them through the “Enrollment Visit Case Report Form.”

The Study Nurse/Nurse Practitioner/Physician will review the contents of the study product kit with the child’s family, review the need to complete the study product at the dose and frequency indicated and teach them how to complete the medication diary to document adherence.

Parents will be educated at the time of their child’s enrollment in the study about the potential sequelae of untreated UTI and the benefits of prompt and adequate treatment. They will be instructed to (1) contact primary care providers and study personnel in the event of intercurrent febrile illness, (2) have their child evaluated within 36 hours by a SCOUT study physician or the child’s primary care provider and (3) have a urine sample obtained to evaluate for the presence of UTI. The study nurses, nurse practitioners and the investigators at each site will be available on a 24-hour basis, through a study-dedicated cellular phone.

Stool specimens will be collected either by inoculation of a sterile dacron-tipped swab into stool in a diaper, or by insertion of a swab into the distal rectum (similar to obtaining a rectal temperature) where it will be held in this position for five seconds.

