For each subject at CHOP who agrees to participate in the Microbiome pilot study, an additional perirectal swab and anal swab will be collected. The additional swabs will be used to determine the composition of the subjects’ microbiome. The anal swab will be collected by brushing the swab back and forth five times against the skin just outside of the rectum. For subjects in diapers, a third swab will be collected from the stool in the diaper if one is available.

Primary care providers will be notified of their patient’s participation in the study via telephone, letter, email or electronic health record message.

CHOP Study Visits

Parents of children recruited at CHOP will be given the option of coming to the Wood building at CHOP, meeting the Study Nurse/Nurse Practitioner/Physician at their local primary care practice site, or having a study staff conduct the study visit in their home.

PITT Study Visits

Children recruited at Children’s Hospital of Pittsburgh will have the study visit conducted at the Primary Care Center of Children’s Hospital of Pittsburgh or at one of the community offices where PITTnet personnel are available.

Subjects will be given appointments at the time of study entry for the Day 11 – 14 Test of Cure Visit and the Day 24 – 30 Outcome Assessment Visit. The Study Nurse/Nurse Practitioner/Physician will explain that during each study visit, the Study Nurse/Nurse Practitioner/Physician will ask a specific series of questions to determine the resolution of UTI related symptoms. These study visits will consist of a verbal clinical assessment (symptom questionnaire) and a targeted pain assessment. For subjects enrolled before Day 5, the Study Nurse/Nurse Practitioner/Physician will explain that verification will be obtained on Day 5 or prior to taking the first dose of SCOUT therapy on Day 6 that the subject remains afebrile and with no worsening of symptoms. Any subject that develops a fever or worsening of symptoms (prior to starting study product) will be withdrawn from

the study and considered an entry failure. These subjects will be treated outside this protocol by a physician not associated with the SCOUT Study per current standard of care or if they prefer the parent(s)/legal guardian(s) can choose to have their child treated by their PCP/pediatrician.

Days Six -Ten (While on the study product: continued antibiotic or placebo):

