differences in microbial carriage and composition between and within subjects over time, we will calculate the UniFrac distance [PMID: 20827291] between all pairs of samples. UniFrac is a measure of the fraction of the evolutionary tree relating all observed taxa that is not overlapping between two samples. To visualize these within- and between-subject differences (beta diversity) and to obtain principal components for subsequent statistical testing, we will perform dimensionality reduction using principal coordinates analysis. To enable tests for shifts in the relative abundance of both broad and specific bacterial taxa with respect to the host factors mentioned above, we will collapse the reference-based OTUs according to taxonomy at the genus and phylum levels using QIIME. This will produce culture-independent fractional observation counts of bacterial taxa in all samples.

We will test for overall differences in microbiome composition between short-course and standard-course antibiotics. To test for associations between individual bacterial taxa and these groups, we will perform non-parametric Mann-Whitney U tests. We will perform a similar test for association of microbiome biodiversity with treatment and between-sample diversity as well as gammaproteobacteria relative abundance.. In all cases the significance of association will be determined after correcting for multiple comparisons using false discovery rate.

Subpopulation Analyses: Treatment effects for the primary and secondary outcome measures will be estimated as differences between proportions and compared for subpopulations defined by age groups, febrile or non-febrile UTI (at original UTI diagnosis), and type of originally prescribed antibiotic. First, proportions will be tabulated as two-sample comparisons and chi-square tests for treatment differences in the outcomes within subgroups will be calculated. Factors where significant differences are observed will be further assessed using logistic regression analysis, assuming that the logistic model fits the data. Goodness of fit test will be reported for model checking. Treatment-by-subpopulation interactions will be tested using likelihood ratio tests. The power of these comparisons is expected to be low for both primary and secondary endpoints. The study is only likely to detect marked differences in treatment effects in these subpopulations.

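### Microbiome pilot: the arm comparisons of diversity and gammaproteobacteria at follow-up are valid but leave out the enrolment swab and the randomisation strata, at a cost in precision that depends on an unstated correlation

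*Protocol*

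**What the plan says.** **Swab schedule.** Protocol 5.1 says of the pilot: "The additional swabs will be collected at each visit". Section 8.2 confirms that enrolment is one of those visits: "For each subject at CHOP who agrees to participate in the Microbiome pilot study, an additional perirectal swab and anal swab will be collected". The same section places that visit "Prior to taking the sixth day of prescribed treatment". For children enrolled before Day 5 dosing is complete, it adds: "The subject would start study product on Day 6 and continue through Day 10".

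**Outcomes.** Section 4.2.1 defines the first microbiome outcome as "Comparison of the overall biodiversity of the gut microbial community, as measured by culture-independent marker gene sequencing at each follow-up visit". The gammaproteobacteria outcome has the same time point. Both are levels at follow-up, not changes from enrolment.

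**Tests.** Section 12.4 states: "To test for associations between individual bacterial taxa and these groups, we will perform non-parametric Mann-Whitney U tests". It continues: "We will perform a similar test for association of microbiome biodiversity with treatment". That sentence goes on to cover between-sample diversity and gammaproteobacteria relative abundance, and a false discovery rate correction follows. No baseline term, stratum term, change score or longitudinal model is named for the two scalar outcomes. Within-child differences over time enter through UniFrac distances and principal coordinates.

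**Strata and SAP.** Protocol 6.4.1 stratifies randomisation within site by fever at diagnosis and by the antibiotic first prescribed. SAP 4.2.4 lists the microbiome endpoints but leaves their analysis to the sub-study investigators.

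**The concern.** The enrolment value is measured before the arms can differ, so it is a legitimate covariate. The plan already provides for processing it: 12.4 computes distances between all pairs of samples and taxon counts in all samples. If a child's diversity at enrolment predicts diversity at follow-up, an unadjusted comparison leaves that predictable part in the error term. The same holds for any spread explained by which antibiotic the child was given or whether the infection was febrile, and both factors were stratified at randomisation. What is at stake is the precision of two exploratory comparisons in a sub-study limited to consenting children at one centre. The trial's primary and secondary analyses are not touched.

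**Working it through.** The documents give no sample size, effect size, standard deviation or correlation for the pilot, so there is no planned figure to reproduce. What follows shows a range under assumptions.

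**Inputs from the documents:** 1:1 allocation (Protocol Summary); swabs at enrolment, Day 11-14 and Day 24-30; arms diverge on Day 6; unadjusted Mann-Whitney-type tests.

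**Assumed inputs:** rho from 0 to 0.7; 15 to 50 children per arm; a difference of 0.5 or 0.8 SD; two-sided 0.05 per test. The protocol states no false discovery level, so the correction is not modelled.

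**Step 1, variance.** Adjusting for a baseline with correlation rho multiplies the residual variance by 1 - rho². At rho 0.5 this is 1 - 0.25 = 0.75, so 25% is removed.

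**Step 2, normal-theory power.** If unadjusted power corresponds to z, adjusted power is Phi((z + 1.96)/sqrt(1 - rho²) - 1.96). For 80% power (z = 0.842) and rho 0.5: 2.802/0.866 - 1.96 = 1.275, and Phi(1.275) = 0.899.

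**Step 3, simulation of the proposed method.** Mann-Whitney was compared with rank ANCOVA (rank of follow-up on arm and rank of baseline), with 6,000 runs per setting.

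| rho | 1 - rho² | Variance removed | 50% power becomes | 80% power becomes | Simulated gain, points | n per arm for 80% power at 0.8 SD |
|---|---|---|---|---|---|---|
| 0 | 1.00 | 0% | 50.0% | 80.0% | within about 1 | 25 |
| 0.2 | 0.96 | 4% | 51.6% | 81.6% | 1-2 | 24 |
| 0.3 | 0.91 | 9% | 53.8% | 83.6% | 1-4 | 23 |
| 0.5 | 0.75 | 25% | 61.9% | 89.9% | 2-12 | 19 |
| 0.7 | 0.51 | 49% | 78.4% | 97.5% | 3-25 | 13 |

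The power columns come from Step 2 and the last column from the normal approximation. The smallest simulated gains at rho 0.5 and 0.7 arise where Mann-Whitney power is already near 97%. Two settings as examples:

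- 20 per arm, 0.8 SD: about 67% with Mann-Whitney; 68%, 70%, 77% and 90% with rank ANCOVA at rho 0.2, 0.3, 0.5 and 0.7.
- 30 per arm, 0.5 SD: about 45% with Mann-Whitney; 47%, 48%, 55% and 71% with rank ANCOVA.

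**Step 4, cost when the baseline is uninformative.** Type I error for rank ANCOVA stayed between 0.045 and 0.057. At rho 0 its power was within about 1 point of Mann-Whitney, even at 15 per arm.

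**Limit of the simulation.** It adjusts for the enrolment value only, not for antibiotic or fever, so it gives neither the gain nor the cost of those terms.

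**The case against.** **The detailed plan may lie elsewhere.** SAP 4.2.4 says sub-study analyses are designed outside the SCOUT protocol, and 12.4 calls itself a general description. A fuller plan may already adjust for baseline. This stands as a limit: the point concerns the protocol text. That text does name tests, however, and the SAP puts nothing in their place.

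**The baseline is not ignored altogether.** A reader might infer that the enrolment swab is wasted. The documents do not support that: 12.4 uses within-child UniFrac distances and carries principal coordinates into later testing. The gap is confined to the scalar comparisons.

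**The enrolment swab is not a pre-treatment value.** It precedes study product, but it is taken on Day 2-6 of the original antibiotic, after differing exposure. In the short-course arm the last antibiotic day is Day 5, so the Day 24-30 swab comes 19 to 25 days later (24 - 5 and 30 - 5). The correlation could be low and could differ between visits. It is also tempting to say that most of the follow-up spread was already present at enrolment, but nothing in the documents shows this.

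**Mann-Whitney is a legitimate test.** A reader might fear that a chance imbalance at enrolment biases the result. It does not: under randomisation the type I error already allows for chance imbalance. Stratified randomisation also balances antibiotic and fever by design, so adjusting for them can only improve precision.

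**Individual taxa are a different problem.** Sparse taxa with many tied zeros do not suit the same adjusted model. This stands, and the fix leaves them alone.

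**Conclusion.** The point holds as a modest, optional gain in efficiency for two exploratory outcomes. As written, 12.4 compares alpha diversity and gammaproteobacteria fraction at follow-up without the enrolment value or the randomisation strata. The tests are valid but may be less precise than the planned samples allow.

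The size is unknown. Under the assumed inputs it is 1-2 points of power at rho 0.2, which is trivial, and up to about 25 points at rho 0.7. These figures rest on the assumed correlation, pilot size and effect, and on a per-test 0.05 before false discovery correction.

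One might go further and call the pilot underpowered. The documents give no size and no power target, so that cannot be concluded; even that the pilot is small is an inference from its name, single centre and separate consent. What can be said is that the risk is lopsided: in the simulation, baseline adjustment cost almost nothing when rho was zero and helped materially when it was moderate.

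**What to change.** In Protocol 12.4, Microbiome pilot study, for alpha diversity and gammaproteobacteria fraction at each follow-up visit:

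- Make the main comparison a rank ANCOVA (or ANCOVA on a suitably transformed scale) of the follow-up value on arm, adjusted for the child's enrolment value, the originally prescribed antibiotic and the fever stratum.
- Keep Mann-Whitney as a sensitivity analysis.
- For a child without a usable enrolment swab, impute the baseline simply and without regard to arm, for example the overall mean plus a missing-value indicator.
- Leave the stated tests for individual taxa, and the false discovery correction, as they are.
- If a separate sub-study plan already adjusts for baseline, cite it and align 12.4 with it.

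Settle this before the sub-study data are examined, so that the choice between adjusted and unadjusted results is not made afterwards.

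The cost is wording and a little extra analysis; no new samples are needed. The covariates use five degrees of freedom (one for baseline, three for four antibiotics, one for fever). With 20 per arm, for example, residual degrees of freedom fall from 40 - 2 = 38 to 33. A missing-value indicator would take one more, as would an added antibiotic level if the pilot includes children randomised while amoxicillin-clavulanate was still a study antibiotic. If the correlation proves low, those few degrees of freedom are the price.
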